6.10.3.2.7. Time to Symptom Improvement

Time to symptom improvement is defined (in days) as:

(Date when symptom improvement status is changed to "Yes" – Infusion Date + 1)

If a patient has not experienced symptom improvement by completion or early discontinuation of study/study treatment, the patient will be censored at the date of their last visit during the treatment and assessment period. If a patient is hospitalized, the patient will be censored at the date of hospitalization.

Time to symptom improvement will be evaluated during the study treatment and assessment period only and will be summarized by treatment and listed. In addition, a graphical presentation of the symptom improvement will be provided using a KM plot.

6.10.3.3. Participant Clinical Status

6.10.3.3.1. COVID-19-Related Hospitalization or Death from Any Cause

Proportion (percentage) of participants who experience any of the following by Day 29 will be analyzed:

- COVID-19-related hospitalization (defined as ≥24 hours of acute care), or
- Death from any cause

The proportion of participants that experience hospitalization or death from any cause by Day 29 will be summarized by treatment in frequency tables and listed.

In addition, the number of participants that experience COVID-19 hospitalization or death from any cause by Day 29 will be analyzed using logistic regression to compare active treatment versus placebo at each dose level. If the number of observed events is less than 5 in any treatment arm an exact test (i.e. Fisher's exact) will be conducted instead of using a logistic regression. Data will not be imputed due to dropouts or missing data.

Proportion (percentage) of participants who experience COVID-19 related hospitalization or death from any cause by Days 22, 60, and 85 will also be analyzed.

The safety population will be utilized to analyze COVID-19-related hospitalization or death from any cause.

Based on the 'Hospitalization Events' eCRF page, a COVID-19-related hospitalization event is defined as an event with:

'Reason for Health Care Visit' of 'Primary Study Condition'

AND

- a 'Health Care Service Type' of:
 - o 'General Ward' or 'ICU'

OR

o 'Emergency Room' with a duration of \ge 24 hours.

6.10.3.3.1.1. Bayesian Modeling for COVID-19-Related Hospitalization or Death From Any Cause

Additionally, a Bayesian sensitivity analysis will be performed. A Bayesian logistic regression model will be fitted to evaluate the success criteria by the Lilly statistics group with the model listed below:

$$r_{ij} \sim Binomial(p_{ij}, 1)$$

$$\log\left(\frac{p_{ij}}{1 - p_{ij}}\right) = \alpha_i$$

Where,

 r_{ij} : is 1 if patient j on treatment i was hospitalized and 0 otherwise α_i : a parameter corresponding to treatment i (with i=1 being the placebo group). and priors:

$$\alpha_1 \sim \pi(\alpha_1)$$

At least 2 priors $(\pi(\alpha_1))$ will be considered for α_1 , a diffuse $N(0,100^2)$ and an informative prior based on available information at the time of analysis.

The safety population will be utilized to analyze COVID-19-related deterioration.

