6.1.1. Analysis Populations

Patient populations are defined in Table PYAH.6.1 along with the analysis to be used to conduct. The treatment groups and inferential comparisons described in Table PYAH.6.1 will be used unless otherwise specified. Also, unless otherwise specified, for all populations/analysis, participants will be analyzed according to the treatment to which they were assigned.

Table PYAH.6.1. Analysis Populations

Population	Description
Entered	Definition: All participants who signed informed consent.
	Purpose: Used for disposition analysis.
	Treatment Groups: None
	Inferential Comparisons: None
Efficacy	Definition: All randomized participants who received study intervention and
	provided at least 1 postbaseline measure viral load measurement. Participants
	will be analyzed according to the intervention to which they were randomized
	(Intention to treat).
	Purpose: Used for efficacy and pharmacodynamic variables analyses.
	Treatment Groups (Short Label):
	Treatment Arms 1-6:
	175 mg LY3819253 and 350 mg LY3832479 (175/350 LY/LY2), 350
	mg LY3819253 and 700 mg LY3832479 (350/700 LY1/LY2), 700 mg
	LY3819253 and 1400 mg LY3832479 (700/1400 LY/LY2), 2800 mg
	LY3819253 and 2800 mg LY3832479 (2800/2800 LY/LY2), 700 mg
	LY3819253 (700 LY), and placebo (Pbo).
	Treatment Arms 7-8:
	700 mg LY3819253 and 500 mg VIR-7831 (700/500 LY/VIR), and
	placebo (Pbo).
	Treatment Arms 9-11:
	175 mg LY3853113 (175 LY3), 175 mg LY3853113 + 700 mg
	LY3819253 + 1400 mg LY3832479 (LY3/LY/LY2), placebo (Pbo)
	Treatment Arms 12-13:
	175 mg LY3853113 (175 LY3) and 175 mg LY3853113 + 700 mg
	LY3819253 + 1400 mg LY3832479 (LY3/LY/LY2)
	Treatment Arm 14:
	175 mg LY3853113 + 700 mg LY3819253 + 1400 mg LY3832479
	(LY3/LY/LY2)
	Additional optional combination arm may be added if decided.
	Inferential Comparisons:
	Treatment Arms 1-6:
	Each LY dose versus placebo
	Treatment Arms 7-8:
	700/500 LY/VIR dose versus placebo
	Treatment Arms 9-11:
	Each LY dose versus placebo
	Treatment Arms 12-14:
	None
Safety	Definition: All participants randomly assigned and who received any amount of
	study intervention. Participants will be analyzed according to the intervention
	they actually received.
	Purpose: Used for safety analyses, analyses of COVID-19-related
	hospitalization or death from any cause.
	Treatment Groups (Short Label):
	Treatment Arms 1-6:
	175 mg LY3819253 and 350 mg LY3832479 (175/350 LY/LY2), 350
	mg LY3819253 and 700 mg LY3832479 (350/700 LY1/LY2), 700 mg

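### Hospitalisation or death is compared between arms by treatment received, and no as-randomised estimate over all dosed participants is planned

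*SAP*

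**What the plan says.** Four parts of the SAP bear on this point.

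- **Default grouping (6.1.1).** The rule is "unless otherwise specified, for all populations/analysis, participants will be analyzed according to the treatment to which they were assigned".
- **Efficacy population (Table PYAH.6.1).** It requires randomisation, dosing and at least one postbaseline viral load. Its participants "will be analyzed according to the intervention to which they were randomized".
- **Safety population (Table PYAH.6.1).** It takes everyone randomised who received any amount of study intervention. For grouping it says: "Participants will be analyzed according to the intervention they actually received". Its purpose line covers safety analyses and also "hospitalization or death from any cause".
- **Clinical outcomes (6.10.3.3).** In 6.10.3.3.1 the number of participants with COVID-19-related hospitalisation or death by Day 29 "will be analyzed using logistic regression to compare active treatment versus placebo at each dose level", with Fisher's exact test if any arm has fewer than 5 events. The section then says: "The safety population will be utilized to analyze COVID-19-related hospitalization or death from any cause". Sections 6.10.3.3.1.1 (Bayesian sensitivity analysis) and 6.10.3.3.2 (composite with emergency room visits) also name the safety population.

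**The concern.** Choosing the safety population settles two separate matters: who is included, and which arm each person is counted in. Including everyone dosed is sensible. The efficacy population would drop a participant who was hospitalised or died before giving a postbaseline viral load, which is the wrong person to lose from this outcome.

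The grouping is a different matter. For an efficacy comparison with p-values, counting people by treatment received gives up part of the protection of randomisation, and the SAP gives no reason for treating these outcomes differently from viral load and symptoms. Any participant given the wrong infusion would be counted in one arm for viral load and in another for hospitalisation. Because events may be few, as the switch to an exact test allows for, the arm in which one event is counted could matter.

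**Working it through.** **Step 1. Which grouping rule applies?** The as-assigned default in 6.1.1 holds only where nothing else is specified. The safety row does specify otherwise, and it names hospitalisation or death in its purpose line. Sections 6.10.3.3.1, 6.10.3.3.1.1 and 6.10.3.3.2 do not restore as-randomised grouping. These outcomes are therefore analysed as treated.

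**Step 2. Does another planned analysis fill the gap?** The only other population listed for these two composites is per-protocol. Three features stop it from doing so:

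- it is used only if there are enough events;
- it is a subset of the efficacy population, so it needs a postbaseline viral load;
- it removes anyone given a medication other than the one randomised.

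It can show whether a result leans on misdosed participants, but it gives no as-randomised estimate over all dosed participants.

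**Step 3. Which arms are affected?** Arms 1-11 have comparisons with placebo. Arms 12-14 are summarised descriptively (6.1.4), so no test is at stake there.

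**Step 4. How large could it be?** The SAP gives no event rate, power or misdosing rate for this outcome, so there is no figure to reproduce. The arm sizes below are the planned ones in 5.2 (122 per arm in Arms 9-11; 150 placebo and 100 in most active arms in Arms 1-6). **The event counts are assumed.** Each row moves one placebo-randomised participant with an event to the active arm because active drug was received. Every table has an active arm with fewer than 5 events, so Fisher's exact test is the test the SAP would use.

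With N participants in all, m of them active, and E events in all, the probability of k events in the active arm is

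P(k) = C(m, k) × C(N − m, E − k) / C(N, E),

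and the two-sided p is the sum of P(k) over all k that are no more probable than the observed one.

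Arms 9-11 (placebo versus active):

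- As randomised, 6/122 versus 0/122: N=244, m=122, E=6. P(0)=0.0147 and, by symmetry, P(6)=0.0147. p = 0.0147 + 0.0147 = **0.029**. Risk difference 6/122 − 0 = 4.9 points.
- As treated, 5/121 versus 1/123: N=244, m=123, E=6. Observed P(1)=0.0888. Also no more probable: P(0)=0.0140 and P(6)=0.0154. P(5)=0.0949 is larger and is left out. p = 0.0888 + 0.0140 + 0.0154 = **0.118**. Risk difference 5/121 − 1/123 = 4.1 − 0.8 = 3.3 points.

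| Assumed, as randomised | p | As treated after one move | p |
|---|---|---|---|
| 6/122 vs 0/122 | 0.029 | 5/121 vs 1/123 | 0.118 |
| 7/150 vs 0/100 | 0.044 | 6/149 vs 1/101 | 0.247 |

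Read from right to left, each row shows the opposite error: an active-randomised participant with an event who was given placebo would turn a non-significant randomised comparison into a significant as-treated one.

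**Step 5. How likely is it?** With no dosing error the two groupings are identical. Moving a participant without an event changes little: 7/150 versus 0/100 stays between p=0.0437 and 0.0443, depending on the direction of the move. If 5% had events and 1% were misdosed (both assumed, neither in the SAP), the expected number of misdosed participants with an event among 150 on placebo is 150 × 0.05 × 0.01 = 0.075, or about 0.08.

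**The case against.** The strongest answer is that this is a deliberate choice with little practical effect. A reader might infer that the SAP contradicts itself, since 6.1.1 says "participants will be analyzed according to the treatment to which they were assigned". It does not: that rule yields wherever something else is specified, and the safety row and 6.10.3.3 agree with each other. A reader might also infer that the SAP expects misallocation, because the per-protocol set excludes people given another medication. That exclusion is a contingency rule and forecasts nothing.

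Other parts of the defence also stand:

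- Treatment is a single dose, centrally assigned and given at the site, and Arms 1-11 are double-blind. A dosing error would not normally follow prognosis, so this is not self-selected crossover.
- Hospitalisation is also summarised under safety in 6.12.5. Appendix 2 exempts certain COVID-19 respiratory events and expected disease progression from adverse event reporting, so as-treated hospitalisation figures have a proper safety use.
- The numerical examples sit at the edge of significance. One placebo event fewer already gives p=0.060 (5/122 versus 0/122) or p=0.084 (6/150 versus 0/100), with nobody moved.

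None of this explains why the efficacy test itself should be as treated. A safety use supports keeping as-treated summaries in 6.12, and the wish to keep early events supports including everyone dosed. Both are compatible with grouping the efficacy comparison by randomised arm.

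**Conclusion.** The point holds as a small, inexpensive improvement. Two secondary efficacy comparisons, and the Bayesian sensitivity analysis of the first, are grouped by treatment received, while the other efficacy outcomes are analysed as randomised. No planned analysis gives the as-randomised result over all dosed participants.

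The effect is probably small or nil, because it arises only if a dosing error occurs and shifts a test materially only if the misdosed participant has an event. The p-value changes shown rest on assumed counts and illustrate fragility; they do not predict a result.

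Two stronger readings are not supported. This is not shown to be the trial's lead clinical outcome: it is listed first among the secondary objectives but is not ranked, and the primary endpoint in Arms 1-11 is viral load. Nor are the arms non-randomised in any general sense, since they coincide with the randomised arms unless someone is misdosed.

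**What to change.** In 6.10.3.3.1, 6.10.3.3.1.1 and 6.10.3.3.2, state that these efficacy comparisons include all participants who were randomised and received any study intervention, analysed by randomised arm, with as-treated grouping as a sensitivity analysis. Amend the purpose line of the safety row in Table PYAH.6.1 to match.

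Do not move these outcomes into the efficacy population as defined, because its postbaseline viral load requirement could drop early events. Leave as-treated grouping in place for all safety analyses in 6.12, including the laboratory, vital-sign, exposure and hospitalisation summaries.

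The cost is a short edit in four places and one extra sensitivity table per composite. No new data are needed and no participant is lost. If no one was misdosed, the two analyses will be identical, and the report can say so in one line.

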6.10.3.3.2. COVID-19-Related Hospitalization, Emergency Room Visit, or Death From Any Cause

Proportion (percentage) of participants who experience any of the following by Day 29 will be analyzed:

- COVID-19-related hospitalization (defined as ≥24 hours of acute care),
- COVID-19 related emergency room visit, or
- death from any cause

The proportion of participants that experience COVID-19 related hospitalization, emergency room visit, or death from any cause by Day 29 will be summarized by treatment in frequency tables and listed.

In addition, the number of participants that experience COVID-19 related hospitalization, emergency room visit, or death from any cause by Day 29 will be analyzed using logistic regression to compare active treatment versus placebo at each dose level. If the number of observed events is less than 5 in any treatment arm an exact test (i.e. Fisher's exact) will be conducted instead of using a logistic regression. Data will not be imputed due to dropouts or missing data.

Proportion (percentage) of participants who experience COVID-19 related hospitalization, emergency room visit, or death from any cause by Days 22, 60, and 85 will also be analyzed.

The safety population will be utilized to analyze COVID-19 related hospitalization, emergency room visit, or death from any cause.

6.11. Pharmacokinetic and Pharmacokinetic/Pharmacodynamic Methods

Pharmacokinetic, pharmacodynamic, and PK/PD analyses are the responsibility of Lilly's PK/PD group.

A summary of LY3853113, LY3819253, LY3832479, and VIR-7831 concentration-time data will be reported in the clinical study report. Population PK model-based analyses, exploratory exposure-response analyses (a.k.a., population PK/PD modeling) of safety, pharmacology, and efficacy may be performed.

6.12. Safety Analyses

Percentages will be calculated using the safety population as the denominator. For events that are sex-specific, the denominator and computation of the percentage will include only participants from the given sex.

Generally, the following statistical methods will be used, unless otherwise noted:

- percentage-based analyses:
 - o p-values based on Fisher's exact test, and
- continuous measurements:
 - p-value based on ANCOVA:
 - model containing terms for treatment,
 - continuous covariate of baseline measurement, and
 - Type III sums of squares will be used.

6.12.1. Baseline and Postbaseline Definitions for Safety Groups

Table PYAH.6.7 provides conceptual definitions of baseline and postbaseline by analysis type.

Table PYAH.6.7. Baseline and Postbaseline Definitions for Safety Groups Initial Controlled Periods of Individual Studies Controlled Integrated Analysis Sets

Analysis Type	Baseline	Postbaseline
TEAEs	Start of screening and ends	Starts after initiation of the first dose and ends
	prior to the first dose.	on or prior to the day of study discontinuation
Treatment-Emergent	Start of screening and ends	Starts after initiation of the first dose and ends
Abnormal Laboratory Values	prior to the first dose.	on or prior to the day of study discontinuation.
and Vital Signs		
	All scheduled and unscheduled	All scheduled and unscheduled measurements
	measurements will be included.	will be included.
Change from Baseline and to	Start of screening and ends	Starts after initiation of the first dose and ends
Last Postbaseline for	prior to the first dose.	on or prior to the day of study discontinuation.
Laboratory Values and Vital		
Signs	The last scheduled nonmissing	Only scheduled visits will be included. The
	assessment recorded prior to	early termination visits are considered
	the date of the first dose.	scheduled visits.

Abbreviation: TEAE = treatment-emergent adverse event.

6.12.2. Extent of Exposure

Exposure to therapy will be represented as the total number of complete and incomplete infusions and will be summarized using descriptive statistics.

6.12.3. Adverse Events

See Appendix 2 for the definitions of AEs and serious adverse events (SAEs).

Adverse events will be coded according to the Medical Dictionary for Regulatory Activities (MedDRA) and summarized by system organ class (SOC), preferred term (PT), severity, and relationship to IP as assessed by the investigator. For each event classification term, the number of subjects experiencing a treatment-emergent AE (TEAE) with that classification term will be tabulated.

Treatment-Emergent Adverse Events

A TEAE is defined as an event that first occurred or worsened in severity after baseline. The MedDRA Lowest Level Term (LLT) will be used in the treatment-emergent computation. The maximum severity for each LLT during the baseline period will be used as baseline. While unusual, it is possible to have a missing severity for events. For events with a missing severity during the baseline period, it will be treated as "mild" in severity for determining treatment emergence. Events with a missing severity during the postbaseline period will be treated as "severe" and treatment emergence will be determined by comparing with baseline severity. Missing severity will be reported as missing, without imputation, for data listing.

Summaries of TEAEs will include the number of participants with at least 1 TEAE for each treatment group. When reporting by SOC and PT, the reports will present the SOC in alphabetical order; while PTs within the SOC will be presented in order of overall decreasing

frequency of occurrence overall. A patient with multiple TEAEs (different PTs) coded to the same SOC will be counted only once for that SOC, but will be counted each time for different PTs within that SOC. A patient with separate events of the same PT will be counted only once in the frequency tables for that PT.

In an overview table, the number and percentage of participants who experienced a TEAE, a SAE, an AE related to study drug, an AE resulting in death, incomplete dose of study treatment, or discontinuation from the study due to an AE will be summarized by treatment. Treatment-emergent AEs may be reported separately for the treatment and assessment period and the follow-up period.

Additional types of AEs to be summarized are described in Table PYAH.6.8.

Table PYAH.6.8. Additional Types of Adverse Events to be Summarized

Event Type	Summary Method	
SAEs	SAEs will be summarized for each treatment arm by SOC and PT.	
	These reports will also include the total number of SAE for each	
	SOC and PT.	
TEAEs Resulting in Death	If there are any TEAEs that result in death, a listing of all deaths will	
	be provided. In addition, a summary table may also be created by PT	
	in order of decreasing frequency of preferred term.	
TEAEs Leading to Study Drug	TEAEs for which the action taken with medication is 'Drug	
Discontinuation	Withdrawal' will be identified as TEAEs that lead to study drug	
	discontinuation. The TEAEs that lead to study drug discontinuation	
	will be summarized for each treatment group by SOC and PT for the	
	safety population. A by-patient listing of the TEAEs that lead to	
	study drug discontinuation will also be provided.	
Treatment-Related TEAEs	Every AE will be assessed by the investigator for its relationship to	
	the randomly assigned study treatment.	
TEAEs by Maximal Severity	Every AE will be graded by the investigator as mild, moderate, or	
	severe, so for each patient the greatest severity observed can be	
	obtained by comparing the severity of all of a patient's TEAEs that	
	share the same SOC or PT. A table of TEAEs by maximal severity	
	will be prepared for each treatment arm by SOC and PT.	
TEAEs (Not Including Serious)	The most common nonserious TEAEs will be summarized. All PT	
	that occur in at least 5% of the safety population participants in any	
	treatment group, when not counting the serious TEAEs, will be	
	tabulated by SOC and PT for each treatment group. These reports	
	will also present the total number of TEAEs for each SOC and PT.	

Abbreviations: AE = adverse event; PT = preferred term; SAE = serious adverse event; SOC = System Organ Class; TEAE = treatment-emergent adverse event.

SOC mapping

Medical Dictionary for Regulatory Activities PTs are assigned to a SOC through primary mappings (defined by MedDRA). Thus, MedDRA PTs will appear in only 1 SOC.

Events not summarized

Events considered related by the investigator will not be summarized for CSR. Medical representatives may use the relatedness assessment when reviewing individual cases.

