Treatment Arms 12-14:

The primary objective is to characterize the safety profile of LY3853113 alone and in combination with LY3819253 and LY3832479 after intravenous infusion for participants with mild to moderate COVID-19 illness who are at a high risk of severe COVID-19 illness and/or hospitalization.

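### SAP Section 6.12.3 both requires and rules out a group summary of adverse events judged related to study drug

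*SAP*

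**What the plan says.** Section 6.12.3 of the SAP deals with relatedness in four places.

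- The opening paragraph has coded adverse events "summarized by system organ class (SOC), preferred term (PT), severity, and relationship to IP as assessed by the investigator".
- The overview table is to give, by treatment, "the number and percentage of participants who experienced a TEAE, a SAE, an AE related to study drug", among other categories.
- The text then states: "Additional types of AEs to be summarized are described in Table PYAH.6.8". One row of that table is headed Treatment-Related TEAEs. Its summary-method cell says only that each event is assessed: "Every AE will be assessed by the investigator for its relationship to" the assigned treatment.
- The last paragraph, under a heading for events that are not summarised, states: "Events considered related by the investigator will not be summarized for CSR". It adds that medical representatives may consult the assessment when they review individual cases.

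For Arms 12-14, Section 4.1 says: "The primary objective is to characterize the safety profile of LY3853113 alone and in combination with LY3819253 and LY3832479 after intravenous infusion", in participants at high risk.

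**The concern.** A programmer who builds the overview table as described breaks the closing sentence. A programmer who obeys the closing sentence leaves out an item that the overview table requires. The SAP does not say which instruction takes precedence, so what the CSR reports on relatedness would be settled at programming, possibly after unblinded data have been seen.

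Most is at stake in Arms 12-14. Safety is their primary objective, Section 5.1.3 assigns them no placebo arm, Table PYAH.6.1 lists no inferential comparison for them, and Section 6.1.4 limits them to descriptive statistics. With no concurrent control to show the background event rate, the investigator's attribution is one of the few pieces of information on whether an event reflects the drug, the infusion or the illness. Section 5.2 also says that Arm 12 was made larger to assess tolerability of undiluted administration, a question on which attribution bears directly.

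**Working it through.** No formula applies. The check is a comparison of the current text with itself; none of it comes from the revision history.

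**Step 1. The instructions side by side (all in Section 6.12.3).**

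| Place | Instruction on related events | Strength |
|---|---|---|
| Opening paragraph | Summarise by "severity, and relationship to IP as assessed by the investigator" | Explicit |
| Overview table | Number and percentage with a related AE, by treatment | Explicit and specific |
| Table PYAH.6.8, Treatment-Related TEAEs row | Listed among types to be summarised; the cell gives no tabulation | By title and lead-in only |
| Closing paragraph | Not summarised for the CSR | Explicit prohibition |

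There are thus two explicit orders, one order implied by a table title, and one prohibition. The first two cannot be carried out in the CSR together with the fourth. The third is weaker. Neighbouring rows state what will be tabulated, while this one stops at the assessment.

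**Step 2. Does other text choose between them?**

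- Section 6.1 says that some displays described in the SAP may be left out of the CSR and that displays not provided are available on request. This is a general permission to omit. It does not decide between a specific order and a specific prohibition.
- Section 6.18 describes the registry output. It splits events by seriousness and preferred term, not by relatedness, so it is not the unstated destination of the related-event summaries.
- The use in case review is optional and individual, so it is not a group summary.

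Nothing resolves the conflict.

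**Step 3. Who is affected?** The closing sentence has no arm restriction, so it covers every arm. The arms with safety as primary objective and no concurrent placebo have these planned sizes (Section 5.2):

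- Arm 12: about 100
- Arm 13: about 50
- Arm 14: about 140
- Sum: 100 + 50 + 140 = 290

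This is the planned enrolment where the choice matters most. It does not measure harm.

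**Step 4. What remains for Arms 12-14 if the closing sentence governs?**

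- TEAEs by SOC and PT, and by maximal severity (Section 6.12.3, Table PYAH.6.8)
- TEAEs leading to study drug discontinuation, by SOC and PT (Table PYAH.6.8)
- Complete and incomplete infusions (Section 6.12.2), and incomplete dosing in the overview table
- Narratives for deaths, SAEs and treatment discontinuations due to AEs (Section 6.12.4)

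The item lost is the by-arm count of events that the investigator judged related.

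**The case against.** The strongest reply is that this is a drafting slip with limited consequence. Several parts of that reply stand.

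- A reader might infer that the related-event count is the only planned group display that could separate drug or infusion effects from COVID-19. The documents do not support that. The displays in Step 4 bear on the same question, and Appendix 2 already keeps expected signs and symptoms of the disease out of the adverse event data unless they are more severe than expected. Appendix 2 also cuts the other way: COVID-19 hypoxemia and respiratory failure become reportable when the investigator deems them related to study drug, so attribution helps decide which events enter the tables.
- A reader might infer that each arm goes from one related-event table to none. The Table PYAH.6.8 row specifies no table, so this cannot be said. What is definite is one overview entry and a general clause.
- A reader might infer that the relatedness data would never reach any group table. The prohibition is worded for the CSR, and Section 6.1 leaves room for displays outside it, although the heading over the closing paragraph points the other way. The data are still collected.
- A reader might infer that all substudies lack a control and so share the problem fully. Section 6.19.1 has their safety data summarised in a similar manner to Section 6.12, so the wording conflict carries over. But Addendum (4) lists a placebo group for every dose.
- Arms 9 and 10 test the same regimens against the placebo of Arm 11. That is indirect evidence for Arms 12-14, limited because Arms 9-11 enrol low-risk participants.
- Leaving investigator attribution out of group tables is a defensible choice, because attribution is subjective, and more so when treatment is known.

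None of this removes the contradiction. A deliberate choice to omit relatedness would still require deletion of the two explicit orders to report it.

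**Conclusion.** The contradiction holds. Section 6.12.3 requires related adverse events to be summarised, including a count in the overview table, and then excludes them from the CSR, and no other section of the SAP settles which applies. If the exclusion governs, the CSR contains no group-level count of related events in any arm. The consequence is greatest for Arms 12-14, about 290 planned participants, for the reasons given above.

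The size is moderate. One safety summary is undetermined. No efficacy estimate, error rate or sample size is touched, and the other safety displays and narratives stay in place. That Arms 12-14 are the most affected is an inference from their objective and design, since the sentence itself singles out no arm. The conclusion assumes that the SAP governs the CSR tables and that no separate document overrides this paragraph.

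**What to change.** Reconcile the passages so that Section 6.12.3 gives one instruction.

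1. Preferred: delete the closing sentence on related events, or narrow it so that the overview count of participants with a related AE is kept at least for Arms 12-14.
2. Complete the Treatment-Related TEAEs row of Table PYAH.6.8 with a method: number and percentage of participants by SOC and PT for each arm.
3. Add a caveat that the investigator's attribution is subjective in open-label arms.
4. If relatedness is deliberately left out for the placebo-controlled arms, say so, and remove the overview entry and the relationship clause in the opening paragraph for those arms.

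The cost is SAP wording and at most one standard table on data already collected. Removing only the conflicting instructions would also cure the inconsistency. That is cheaper, but it would leave the uncontrolled safety arms without the related-event count.
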